8.2.6.2. ITT Analyses of OCR at Outcomes Assessment Visit #2

Twenty (20) multiple imputation datasets for OCR at Outcome Assessment Visit #2 will be generated in manner analogous to that described in 8.2.1, except using OCR at Outcome Assessment Visit #2 in place of DOOR at Outcome Assessment Visit #2 for the response. Also, analogous to 8.2.1, the Mann-Whitney U statistic will be computed for each of the datasets and combined using Rubin’s Rules to generate the test statistic W and a p-value for the test of the null hypothesis that

$$\Pr(\text{OCR at Outcome Assessment Visit \#2 is better in short course}) + 0.5 \Pr(\text{OCR at Outcome Assessment Visit \#2 is equal}) = 0.5.$$

The F-test using the W statistic will be inverted to produce a 95% confidence interval for $\Pr(\text{OCR is better in short course}) + 0.5 \Pr(\text{OCR is equal})$. Whether the lower bound of this confidence interval is greater than 0.4 will serve as a test of the non-inferiority null hypothesis that

$$\Pr(\text{OCR at Outcome Assessment Visit \#2 is better in short course}) + 0.5 \Pr(\text{OCR at Outcome Assessment Visit \#2 is equal}) < 0.40.$$

Results will be reported in [Table 31](#).

8.2.6.3. Complete Case Analysis of the OCR at Outcome Assessment Visit #1

Analysis will be performed as described in Section 8.2.6 using the CC-V1 population. Results will be reported in [Table 32](#) and [Table 33](#).

8.2.6.4. Complete Case Analysis of the OCR at Outcome Assessment Visit #2

Analysis will be performed as described in Section 8.2.6 using the CC-V2 population. Results will be reported in [Table 34](#) and [Table 35](#).

8.2.6.5. According-to-Protocol Analysis of the OCR at Outcome Assessment Visit #1

Analysis will be performed as described in Section 8.2.6 using the ATP-V1 population. Results will be reported in [Table 36](#) and [Table 37](#).

8.2.6.6. According-to-Protocol Analysis of the OCR at Outcome Assessment Visit #2

Analysis will be performed as described in Section 8.2.6 using the ATP-V2 population. Results will be reported in [Table 38](#) and [Table 39](#).

8.2.6.7. Worst Case Analysis of the OCR at Outcome Assessment Visit #1

Analysis will be performed as described in Section 8.2.6 using the ITT population with missing values imputed as follows. Subjects in the short course arm will have their ordinal clinical response imputed as 8. As an exception, subjects in the short course arm with OCR missing for Outcome Assessment Visit #1 but not for Outcome Assessment Visit #2 will have the OCR for Outcome Assessment Visit #1 imputed as the Outcome Assessment Visit #2 value or as 5, whichever value is larger. Subjects in the standard course arm will have their ordinal clinical response imputed as the value that would occur if all missing data was benign (no additional solicited events / cough / fever, etc.). Results will be reported in [Table 40](#).

8.2.6.8. Worst Case Analysis of the OCR at Outcome Assessment Visit #2

Analysis will be performed as described in Section 8.2.6 using the ITT population with missing values imputed as follows. Subjects in the short course arm will have their ordinal clinical response imputed as 8. Subjects in the standard course arm will have their ordinal clinical response imputed as the value that would occur if all missing data was benign (no additional solicited events / cough / fever, etc.). Results will be reported in [Table 41](#).

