11.4.2 Secondary Analyses

All secondary and exploratory analyses will use a Type I error rate of 0.05 and will not correct for multiple comparisons. All tests will be two-sided.

Secondary analyses will include:

- Analysis of DOOR at Outcome Assessment Visit #2, performed as ITT in an analogous manner to the primary analysis.
- Sensitivity Analyses for the DOOR at Outcome Assessment Visits #1 and #2 ITT analyses. (1) CC analyses. (2) ATP analyses. (3) Worst case analyses: all imputations of missing data will be the worst case (result in the lowest possible DOOR given available information) for subjects in the 5-day arm and best case for subjects in the 10-day arm. Sensitivity analyses will test the null hypothesis using the Mann-Whitney U Test, estimate using U divided by the number of pairwise comparisons, and will compute confidence intervals by (1) inverting the Mann-Whitney U Test and (2) using a non-parametric bootstrap.
- Separately for Outcome Assessment Visit #1 and #2, using CC cohorts, a forest plot of 95% confidence intervals for the risk difference of each solicited event and the risk difference of any solicited, for each severity threshold (mild or greater, moderate or greater, or severe). Tests for differences in proportions between treatment arms will be given by Fisher's exact tests.
- Separately for Outcome Assessment Visit #1 and #2, using CC cohorts, a forest plot of 95% confidence intervals for the risk difference of lack of resolution of symptoms as well as the following: (1) Oral, rectal, axillary or tympanic temperature $\geq 38.3^{\circ}\text{C}$ (100.9°F), confirmed by repeat measurement after at least 15 minutes, in the 24 hours preceding the Outcome Assessment Visit, unless attributed to a new process that is unrelated to the prior diagnosis of pneumonia; (2) Elevated respiratory rate (RR >50 breaths/minute for children <24 months of age and >40 breaths/minute for children 24-71 months of age) at the time of the Outcome Assessment Visit; and (3) Presence of cough Grade 2 or 3 at the Outcome Assessment Visit. Tests for differences in proportions between treatment arms will be given by Fisher's exact tests.

-

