6.5. Missing Data

While all efforts will be made to minimize missing data, some missing data is expected. Whenever possible, subjects terminating from the study early will be given an early termination visit during which the available components of the DOOR and related measures can be recorded. The primary analysis will use multiple imputation with linear models to impute values using available information (treatment, randomization strata variables, and available visit information), assuming a missing at random (MAR) model. Secondary analyses will further examine the robustness of this analysis, including a “worst case analysis” in which all imputations of missing

data will be the worst case (result in the lowest possible DOOR given available information) for subjects in the 5-day arm and best case for subjects in the 10-day arm. Day 1 in this study is defined as the date of first receipt of study product. If a subject has no record of study product administration or did not receive a first dose of study product, but has other post-randomization data, Day 1 will be imputed as the date 5 days after the date of first receipt of initial antibiotic.

In some cases, a subject may have DOOR defined despite missing some of its components, in which case the subject will be eligible for inclusion into the CC and ATP analysis populations. In analyses of the components of the DOOR using the CC and ATP analysis populations, data will be analyzed as available and missing data will not be imputed.

The study includes several composite variables with rules for assignment, missingness, and imputation described below.

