6.5.4. Most Severe Solicited Event at OAV#1 and OAV#2

The maximum severity at OAV #1 will be calculated based on the following rules:

- If a subject has missing data for the severity grade of any solicited event for two consecutive days or has missing data for more than two days from Day 1 to Day 5 then the most severe solicited event at OAV#1 will be missing.
- Otherwise if a subject has missing data for one or two non-consecutive days from Day 1 to Day 5 then the missing severity will be imputed as the maximum severity grade taken across the previous day and the day after the day with a missing severity. As a special case, for subjects missing severity for Day 1, the missing severity will be imputed as the Severity from Day 2. For subjects missing severity at Day 5 but not missing severity at Day 6, the missing severity will be imputed as the maximum of severity gradings from Day 4 and Day 6. For these subjects with severity grades (0 to 3) recorded or imputed for every solicited event (irritability, vomiting, diarrhea, allergic reaction, stomatitis, and candidiasis) from Day 1 to Day 5, inclusive, the most severe solicited event at OAV#1

will be the maximum severity grade taken across all solicited events from Day 1 to Day 5.

- If a subject had any solicited event of severity grade 3 from Day 1 to Day 5, then the most severe solicited event at OAV#1 will be grade 3, regardless of the presence of missing data during that period.

In a similar manner, the maximum severity at OAV #2 will be calculated based on the following rules:

- If a subject has missing data for the severity grade of any solicited event for more than three consecutive days or has missing data for more than five days from Day 1 to Day 18 then the most severe solicited event at OAV#2 will be missing.

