8.2.2.5. Worst Case Analysis of the DOOR at Outcome Assessment Visit #1

Analysis will be performed as described in Section 8.2.2 using the ITT population with missing values imputed as follows. Subjects in the short course arm will have their ordinal clinical response imputed as 8 and their number of days of antibiotic use imputed if missing (see Section 6.5.6) as 0. As an exception, subjects in the short course arm with OCR missing for Outcome Assessment Visit #1 but not for Outcome Assessment Visit #2 will have the OCR for Outcome Assessment Visit #1 imputed as the Outcome Assessment Visit #2 value or as 5, whichever value is larger. Subjects in the standard course arm will have their ordinal clinical response imputed as the value that would occur if all missing data was benign (no additional solicited events / cough / fever, etc.) and their number of days of antibiotic use imputed if missing (see Section 6.5.6) as 5.

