8.2.2.6. Worst Case Analysis of the DOOR at Outcome Assessment Visit #2

Analysis will be performed as described in Section 8.2.2 using the ITT population with missing values imputed as follows. Subjects in the short course arm will have their ordinal clinical response imputed as 8 and their number of days of antibiotic use imputed if missing (see Section 6.5.6) as 0. Subjects in the standard course arm will have their ordinal clinical response imputed as the value that would occur if all missing data was benign (no additional solicited events / cough / fever, etc.) and their number of days of antibiotic use imputed if missing (see Section 6.5.6) as 5.

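### The Visit #2 worst-case rule scores short-course children who were seen alive as deaths, which contradicts the plan's own definition of worst case

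*SAP*

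**What the plan says.** Both documents define the worst case in the same terms. Protocol 11.4.2: "all imputations of missing data will be the worst case (result in the lowest possible DOOR given available information". SAP 6.5 repeats it: "data will be the worst case (result in the lowest possible DOOR given available information". In both, this applies to the 5-day arm, and the 10-day arm gets the best case.

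The OAV#2 rules do not carry the definition through. SAP 8.2.6.8 (OCR): "Subjects in the short course arm will have their ordinal clinical response imputed as 8". SAP 8.2.2.6 (DOOR) opens the same way: "Subjects in the short course arm will have their ordinal clinical response imputed as 8 and their number of days of antibiotic use". Neither section has an exception. Both complete the standard arm by supposing that whatever is missing was benign, so that arm's recorded data are used.

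OAV#1 differs. SAP 8.2.2.5 and 8.2.6.7 contain an exception for short-course children: "As an exception, subjects in the short course arm with OCR missing for Outcome Assessment Visit #1 but not for Outcome Assessment Visit #2". For them the OAV#1 value is "imputed as the Outcome Assessment Visit #2 value or as 5, whichever value is larger".

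One route to a missing OCR is a diary gap. Under SAP 6.5.4 the solicited-event grade at OAV#2 is missing if data are absent "for more than three consecutive days or has missing data for more than five days from Day 1 to Day 18".

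**The concern.** A short-course child comes to OAV#2, has had no visit or hospitalization for pneumonia, and has no fever, fast breathing or grade 2–3 cough. The diary has four blank days in a row. OCR is then missing, and the worst-case rule records a death. The worst outcome the data allow is a grade 3 solicited event, OCR 4.

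Two outputs are affected directly. Table 41 prints a Yes/No non-inferiority verdict according to whether the lower bound exceeds 0.40. Figure 22 plots the cumulative OCR difference between arms. The OAV#2 worst-case DOOR row in Table 17 uses the same OCR values. SAP 13 declares no change from the analyses planned in the protocol, so this is not presented as a deliberate departure.

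**Working it through.** **1. Which children are capped.** SAP 6.5.5 assigns 8 to deaths first. After that, OCR at OAV#2 can be missing by three routes:
- ACR missing.
- ACR yes, resolution of symptoms missing. The worst possible value is 5.
- ACR yes, symptoms resolved, solicited-event grade missing. The worst possible value is 4.

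SAP 6.5.1 allows ACR yes only if the child received study product, did not die during participation and had OAV#2. On the second and third routes death is therefore excluded by the recorded data, and 8 is impossible.

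**2. Inputs.** From SAP 5: 200 per arm, and about 10% loss. (The Noether formula there gives (1.960 + 1.282)² / (12 × 0.25 × 0.1²) = 350.2 against the stated 360, and 360/0.9 = 400, so the plan's size is reproduced.) From Table 41: margin 0.40. The documents give no OCR distribution and no diary-gap rate, so both are assumed below. The distribution is the same in both arms.

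**3. Effect on the estimate.** Let P = Pr(OCR better in short course) + ½ Pr(equal). Let f be the missing fraction in each arm, with missing standard-arm children set to OCR 1 and all missing short-course children capped at 4. A child scored 8 loses to everyone except another 8. Scored 4, the child beats OCR 5–8 and ties with 4. So

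fall in P from scoring 8 = f(1−f) × [Pr(OCR ≥5) + ½Pr(OCR 4) − ½Pr(OCR 8)].

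For a cap of 5, replace the bracket by Pr(OCR ≥6) + ½Pr(OCR 5) − ½Pr(OCR 8).

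**4. Effect on the bound.** Lower bound = P − 1.96√V/(n₁n₂), with V = (n₁n₂/12)[(N+1) − Σ(M³−M)/(N(N−1))]. The divisor N(N−1) is the usual tie correction. The SAP prints the tie term without it, which gives a negative variance here.

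Example: 80/6/3/1/8/2% in OCR 1–6, f = 10%. As written, P = 0.9 × (0.9×0.5 + 0.1×0.5×0.8) = 0.441. The half-width is 0.0417, so the bound is 0.399. Capped at 4, P rises by 0.09 × (0.10 + 0.005) = 0.0095 and the bound is 0.409.

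| OCR 1/2/3/4/5/6/7 (%) | OCR ≥5 | Fall in P | Bound, scored 8 | Bound, capped at 4 | Above 0.40? |
|---|---|---|---|---|---|
| 90/5/2/0/2/1/0 | 3% | 0.0027 | 0.4113 | 0.4140 | both |
| 80/6/3/1/8/2/0 | 10% | 0.0095 | 0.3993 | 0.4087 | changes |
| 65/15/6/2/8/3/1 | 12% | 0.0117 | 0.3855 | 0.3972 | neither |
| 65/5/5/5/15/5/0 | 20% | 0.0203 | 0.3855 | 0.4058 | changes |
| 45/23/10/2/13/5/2 | 20% | 0.0189 | 0.3717 | 0.3906 | neither |
| 40/20/8/2/20/8/2 | 30% | 0.0279 | 0.3687 | 0.3966 | neither |

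At 5% missing per arm every one of these distributions passes under both rules. At 15% every one fails under both.

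**5. How wide the window is.** With 5% to 30% of children at OCR ≥5 (and 60% to 40% at OCR 1), equal loss in both arms and a cap of 4, the verdict changes only at 15 missing per arm (5% case) or at 12–18 (30% case). If the standard arm is complete, the window is 20–22 missing short-course children (5% case) to 19–47 (30% case). With a cap of 5 the windows are narrower.

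**6. Figure 22.** If a fraction f of the short arm is capped at 4, scoring 8 moves the cumulative difference by f at each of OCR ≤4 to ≤7. That is 10 percentage points at f = 10%.

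**The case against.** The strongest reply is that the rule errs only against short course. It cannot create a false claim in its favour: non-inferiority met under this rule would also be met under the correct one. The primary multiple-imputation analysis and the CC and ATP analyses are untouched, and Protocol 11.4.2 makes OCR non-inferiority analyses optional. All of this stands, and it limits the consequence.

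Three stronger readings are tempting and are not supported.

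- A reader might infer that both visits treat every missing short-course OCR as a death. At OAV#1 they do not, because the exception in SAP 8.2.2.5 and 8.2.6.7 covers any child with a known OAV#2 OCR. Nor would OAV#1 data alone justify a cap: SAP 6.5.5 scores a death at any point of participation as OCR 8 at OAV#1 too, so a child well at OAV#1 and then lost could still be an 8.
- A reader might infer that the planned 10% missing is the number affected. That 10% is loss to follow-up. A child without OAV#2 has missing ACR, and no cap of 4 or 5 applies. The tables above assume every missing child is capped, so they show the largest effect for the stated distributions.
- A reader might infer that the rule generally reverses the non-inferiority verdict. It does so only in some assumed distributions and within limited ranges of missingness.

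**Conclusion.** The inconsistency is real at OAV#2. For children seen at the final visit with ACR yes and an incomplete component, SAP 8.2.2.6 and 8.2.6.8 assign a value that the recorded data exclude and that the plan's own definition does not permit. The two arms also follow different logic.

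The size is modest. With 200 per arm, 10% missing in each arm, all short-course missing capped at 4, and 3% to 20% of children at OCR 5 or worse, the bound falls by about 0.003 to 0.02 (0.028 if 30% are at OCR 5 or worse). The Table 41 verdict changes only when the bound already lies close to 0.40. These figures rest on assumed OCR distributions and shrink in proportion if only some of the missing children are capped. The distortion of Figure 22 occurs whenever any capped child is scored 8.

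At OAV#1 the remaining defects are small. The floor of 5 is too harsh where a child known to have survived has ACR yes and resolved symptoms at OAV#1. A child seen alive at OAV#2 whose OAV#2 OCR is also missing still receives 8.

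The point concerns the OCR value only, not the imputation of antibiotic days. It should be corrected, but it does not threaten the primary result.

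**What to change.** In SAP 8.2.2.6 and 8.2.6.8, impute a missing short-course OCR as the worst value compatible with the recorded components:
- 4 if ACR is yes and symptoms are resolved.
- 5 if ACR is yes and resolution is missing.
- 7 if ACR is missing but the child is known alive at the end of participation.
- 8 only if survival is unknown.

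The step from 8 to 7 is for consistency; in the distributions above it moves the bound by 0.001 or less.

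In SAP 8.2.2.5 and 8.2.6.7, keep the existing exception and make two changes. Extend it to children known alive at OAV#2 whose OAV#2 OCR is missing, using their OAV#2 worst-case value from the list above. Lower the floor from 5 to 4 where OAV#1 ACR is yes and symptoms are resolved. Do not cap on OAV#1 data alone.

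The cost is SAP wording and a short derivation, with no new data. The worst case becomes less extreme, as its definition requires.

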8.2.7. Additional Analysis of Cough

The proportion of subjects in each treatment group experiencing moderate or severe cough will be tabulated by day from Day 1 to Day 25 (as recorded from the memory aid), by visit, and overall, with 95% exact confidence intervals ([Table 42](#)). The proportion of subjects in each treatment group experiencing cough will also be tabulated by day from Day 1 to Day 25 (as recorded from the memory aid), by visit, and by severity level ([Table 43](#) and [Table 44](#)). Finally, cough will be analyzed by taking the most severe response over the follow-up period, dichotomizing into a binary variable (none or mild versus moderate or severe) ([Table 45](#)). Proportions for these derived binary variables will be reported along with 95% exact confidence intervals. Comparisons of proportions by treatment groups will be given as odds ratios (with

95% exact confidence intervals) and p-values from Fisher's Exact Tests. Cough severity will be listed by study day and study visit ([Listing 15](#) and [Listing 16](#)).

8.3. Exploratory Efficacy Analyses

8.3.1. Complete Case Evaluation of DOOR at Outcome Assessment Visit #1, Minimum Required Difference in Days for Antibiotic Use "Tie-breaking" Varies $k=1,2,3,4,5$, or infinity

In the primary RADAR/DOOR analysis, if two subjects from separate treatment arms have an equal ordinal clinical response but a difference in the duration of antibiotic use of at least $k=1$ day, RADAR assigns a more favorable response to the subject with fewer days of antibiotic use. For a sensitivity analysis, the effect of increasing the minimum difference in the duration of antibiotic use ($k=2,3,4$, or 5 , or infinity) before a favorable response is given to the subject with shorter duration of antibiotic use will be explored. The analysis of RADAR/DOOR with $k=\text{infinity}$ is equivalent to comparison of OCR without regard for number of days of antibiotic use, and is included here for comparative purposes. For each value of k , bootstrapped confidence intervals of the probability of more favorable DOOR due to assignment to the 5-day antibiotic course will be computed and plotted versus k . Analysis will be performed separately for DOOR at Outcome Assessment Visit #1 and DOOR at Outcome Assessment Visit #2. Analyses will be performed using CC-V1/CC-V2 cohorts. Results will be reported in [Table 46](#) and [Figure 23](#).

8.3.2. Stratified (ITT) Analyses of DOOR at Outcome Assessment Visit #1

Analysis of DOOR at Outcome Assessment Visit #1 as described in Section 8.1.1 will be performed separately for each level of each stratification variable (e.g. an analysis of all subjects of age <24 months at enrollment, and a separate analysis of all subjects of age 24-71 months at enrollment) and by clinical site. Results will be reported [Table 47](#).

8.3.3. As Treated Analysis of Effect of Number of Days of Antibiotic Use on OCR at Outcome Assessment Visit #1 and Outcome Assessment Visit #2

The analysis will be performed using the subset of the CC-V1 analysis population that did not receive off-study systemic antibiotic unrelated to pneumonia prior to Outcome Assessment Visit #1. The justification for excluding subjects with unrelated antibiotic use is that subjects receiving unrelated antibiotics are at risk for both improved outcomes due to ongoing antibiotic use as well as increased side effects related to antibiotics administration. The effect of the number of days of antibiotic use at Outcome Assessment Visit #1 on OCR at Outcome Assessment Visit #1 will be analyzed using a proportional odds model that simultaneously uses all cumulative logits (Agresti 2003).

Let \mathbf{K} be the set of distinct OCR values observed at Outcome Assessment Visit #1, with the exception that the highest (worst) distinct value observed is not included in the set.

Let Y_i = the OCR of subject i at Outcome Assessment Visit #1.

Let X_i = the number of days of antibiotic use at Outcome Assessment Visit #1 for subject i .

α_k , where $k \in \mathbf{K}$, and β are parameters to be simultaneously estimated through maximum likelihood methods.

Then, proportional odds model with cumulative logits is defined as

$$\text{Logit } [P(Y_i > k)] = \alpha_k + \beta X_i, \quad k \in \mathbf{K}$$

The following gives the interpretation of the model. Suppose D is any non-negative integer.

$$\text{Then, } \log[\text{odds}(\text{OCR} > k \mid X_i = D+1) / \text{odds}(\text{OCR} > k \mid X_i = D)] = \beta.$$

That is, for any k , where k is from the set of observed OCR values at Outcome Assessment Visit #1 besides the highest observed value, e^β gives the odds ratio of an OCR at Outcome Assessment Visit #1 greater than k for the effect of one additional day of use of antibiotic.

It should be stated clearly that this analysis is “as treated” rather than “as randomized.” As such, causality cannot be inferred from a statistically significant association. This is especially true if subjects receiving off-study antibiotic not unrelated to the prior diagnosis of pneumonia are observed during the study. Such subjects will have a higher OCR and will also likely have more days of antibiotic use.

This analysis will be repeated using the subset of the CC-V2 analysis population that did not receive off-study systemic antibiotic unrelated to pneumonia prior to Outcome Assessment Visit #2. The effect of the number of days of antibiotic use at Outcome Assessment Visit #2 on OCR at Outcome Assessment Visit #2 will be analyzed using logistic regression with a proportional odds assumption. Results from both analyses will be summarized in [Table 48](#). The odds ratio for the proportional odds of an OCR at Outcome Assessment Visit #1 greater than k for the effect of one additional day of use of antibiotic will be reported with a 95% Wald confidence interval and p-value from a Wald test. For $p < 0.05$, an association between OCR and the number of days of antibiotic use, as treated, will be concluded.

